2.2. Study Design

This is a Phase 2, 24-week, multicenter, randomized, double-blind, 5-arm, parallel group, active comparator study to evaluate the efficacy and safety profiles of 2 combinations of investigational products (IPs): PF-06650833 co-administered with PF-06651600 (PF-06650833 + PF-06651600) and PF-06650833 co-administered with tofacitinib (PF-06650833 + tofacitinib), as well as the efficacy and safety of each IP individually in the absence of background MTX in participants with moderately - severely active RA who have had an inadequate response to MTX (MTX-IR). Both PF-06650833 and tofacitinib will be administered as modified release (MR) tablets to allow for once daily administration. The primary objective is to demonstrate superiority of at least 1 combination to tofacitinib monotherapy as measured by CFB in DAS28-CRP at Week 12. A key secondary endpoint is to assess the remission rates of the combinations and individual IPs at Week 24, as defined by DAS28-CRP <2.6. The study is powered to show statistical superiority of the combinations to tofacitinib monotherapy at Week 12.

[figure not shown]
After an up to 28-day screening period, eligible participants will enter a 24-week active treatment period after being randomly assigned to one of the 5 treatment groups shown in [Figure 1](#) below.

All doses will be administered orally once daily in a fasted state (about 4 hours after the last and 1.5 hours before the next meal). In order to maintain the blind and minimize bias, all participants will receive the same number and types of tablets each day as a mix of active and placebo tablets. MTX (and folate/folinic acid taken with MTX) will be discontinued at the time of randomization and washed out during the active treatment phase. The MTX washout is intended to reduce the potential for excessive immune suppression and additive safety liability.

No changes in the background concomitant steroid dose is allowed during the study. During the active dosing period, no “rescue” treatment is pre-specified. However, limited - duration increases in permitted analgesic medication (acetaminophen/paracetamol, nonsteroidal anti-inflammatory drugs [NSAIDs], opiates) will be permitted for acute worsening of arthritis pain (see Permitted Concomitant Medications, Protocol Sections 6.5.1 and 6.5.2).

Up to approximately 450 participants are planned to be randomized globally into the study to ensure at least up to approximately 370 participants complete at least 12 weeks of active dosing (assuming a dropout rate of approximately 18%). Participants will be in this study for a total of approximately 32 weeks which includes an up to 28-day screening period, a 24-week active treatment period, and a 4-week drug-free follow-up period.

Figure 1. Study Design Schematic

3. ENDPOINTS AND BASELINE VARIABLES: DEFINITIONS AND CONVENTIONS

3.1. Efficacy Endpoints

The characterization of the treatment efficacy at a given visit relies on the four classes of outcomes

- Clinician Reported Outcomes (ClinRO);
- Patient-Reported Outcomes (PRO);
- Laboratory Measurements (LAB);
- Imaging Measurements (IMG).

The endpoints are designated as primary, secondary, **CCI** in Table 2 in Section 2.1. This section further defines the components of the composite endpoints.

3.1.1. Clinician Reported Outcomes (ClinRO)

The outcomes include:

- Counts of Tender/Painful Joints (**TJC28, TJC68**) among the pre-defined sets of 28 (TJC28) and 68 (TJC68) joints. The 28-joints set is the subset of 68 joints set. Higher scores indicate higher level of disability.
- Counts of Swollen Joints (**SJC28, SJC66**) among the pre-defined sets of 28 (SJC28) and 66 (SJC66) joints. The 28-joints set is the subset of 66 joints set. Higher scores indicate higher level of disability.
- Physician Global Assessment Score (**PhGA**) is defined as a value within (0-100 mm or 0-10 cm) visual analog scale. Higher scores indicate higher level of disability.

3.1.2. Patient-Reported Outcomes (PRO)

The outcomes include:

CCI

3.1.3. Selected Laboratory Measurements (LAB)

The following laboratory measurements used in the computation of the efficacy endpoints are included below:

- CRP- concentration of high sensitivity C-reactive protein (mg/L). The normal range is 0.08-3.1 mg/L. Higher values of CRP indicate higher levels of inflammation.
- ESR- Erythrocyte Sedimentation Rate (mm/hr). The normal range is 0 to 22 mm/hr for men and 0 to 29 mm/hr for women. Higher values of ESR indicate higher level of inflammation.

3.1.4. Imaging Measurements (IMG)

The MRI imaging endpoints come from the dynamic contrast-enhanced MRI (DCE-MRI), RA MRI scoring system (RAMRIS) and automated quantitative RA MRI system (RAMRIQ)

- The DCE-MRI method provides 5 measurements of interest: Volume of enhancing synovium, Mean Ktrans, Median Ktrans, Median AUCBN (90), and Median Ve. Each of these values will be reported for 4 different subregions (*metacarpophalangeal joints, wrist joint, hand, wrist and metacarpophalangeal joints*) resulting in 20 endpoints for a study participant at each visit.
- The RAMRIS method provides 5 measurements/scores: bone erosion, synovitis, osteitis/bone marrow edema, tenosynovitis, and joint space narrowing. Bone erosions, Synovitis and Joint space narrowing will be summarized as *combined wrist and MCP locations*. Osteitis/bone marrow edema scores will be shown for the *combined wrist and MCP locations* in addition to *MCP joint locations* and *wrist locations*. Tenosynovitis scores will be shown for the *combined wrist and finger joint locations* in addition to *finger joint locations* and *wrist locations*. This results in 9 endpoints for a study participant at each visit.
- The RAMRIQ method provides 4 measurements/scores: bone erosion, synovitis, osteitis/bone marrow edema, and tenosynovitis. Bone erosions and synovitis will be summarized as *combined wrist and MCP locations*. Osteitis/bone marrow edema scores will be shown for the *combined wrist and MCP locations* in addition to *MCP joint locations* and *wrist locations*. Tenosynovitis scores will be shown for the *combined wrist and finger joint locations* in addition to *finger joint locations* and *wrist locations*. This results in 8 endpoints for a study participant at each visit.

Table 4 lists ClinRO, PRO and LAB measurements used in the evaluation of the treatment efficacy.

Table 4. ClinRO, PRO and LAB Outcomes

Outcome	Desirable Score (indicates lower level of disability/inflammation)	Group
TJC28, TJC68	Low	ClinRO
SJC28, SJC66	Low	ClinRO

CCI

CRP	Low	LAB
CCI		

Some of the ClinRO and PRO outcomes and LAB measurements listed in the Table 4 are used for forming composite variables. If any of the component of the score is missing, then the composite score is assigned to a missing value.

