8.1.2.1. Disease Activity Score (DAS) Assessments

[figure not shown]
The Disease Activity Score (DAS) assessment is a continuous composite measure of TJC, SJC, PhGA, and an acute phase reactant that is either CRP CCI. The DAS is derived using differential weighting given to each component. DAS28 is a measure based on assessment of 28 joints for tenderness and swelling (tender and swollen joint counts). DAS28 will be calculated with 4 components (TJC, SJC, PtGA, and either CRP CCI [DAS28-CRP CCI]). The formulae for calculation of DAS28-CRP, CCI are presented in the [Appendix 10](#).

Remission and low disease activity were defined as scores <2.6 and ≤ 3.2 , respectively for DAS28-CRP.

[figure not shown]

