9.4.1. Efficacy Analyses

Endpoint	Statistical Analysis Methods
Primary: Change from Baseline DAS28-CRP at Week 12	A Mixed Model Repeated Measures (MMRM) approach to estimate the mean change from baseline of DAS28-CRP at Week 12 using data at all visits post-baseline up to Week 12 to estimate the effect of the initially randomized treatment at Week 12. The analysis will use the mITT analysis set Missing data will not be imputed for this analysis. The MMRM analysis will contain fixed effect terms for treatment, scheduled study visit, baseline DAS 28-CRP, treatment by visit interaction, baseline by visit interaction. The model will use an unstructured covariance matrix. The primary analysis, comparing the combination arm to the tofacitinib monotherapy arm will be done using estimated least squares means for each treatment arm at Week 12. The comparison will be made at the one-sided significance level of 0.05 and no adjustment for multiplicity of comparisons will be attempted.
Key Secondary: DAS28-CRP Remission at Week 24	A landmark analysis at Week 24 will estimate the relative risk of DAS 28-CRP remission comparing each combination arm to the tofacitinib monotherapy arm. This analysis will use the mITT analysis set and the non-responder imputation method (NRI). The NRI treats missing value of the binary outcome as non-response with the exception of the two special cases of the reason for missing data. These special reasons are missingness related to the COVID infection (either patient illness or COVID-related problem of attending the visit) and missingness when subject attended the visit but some of the components for the calculation of the outcome (eg, ACR20) are missing. The observations that are missing for these special reasons will be excluded from the calculation of the probabilities of response at a given visit. Exact statistical inference will be used. The comparison will be made at the one-sided significance level of 0.05 and no adjustment for multiplicity of comparisons will be attempted.
Other Secondary CCI	Will be described in the SAP finalized before database lock.

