3.1.5. Continuous Composite Measures of Efficacy: DAS28-CRP, DAS28-ESR, CDAI, SDAI

Table 5. Continuous Composite Outcomes

Variable	Calculation
DAS28-CRP	$0.56\sqrt{TJC28} + 0.28\sqrt{SJC28} + 0.36\ln(CRP, mg/l + 1) + 0.014PtGA(mm) + 0.96$
DAS28-ESR	$0.56\sqrt{TJC28} + 0.28\sqrt{SJC28} + 0.70\ln(ESR, \frac{mm}{hr}) + 0.014PtGA(mm)$
CDAI	$TJC28 + SJC28 + PtGA(cm) + PhGA(cm)$
SDAI	$TJC28 + SJC28 + PtGA(cm) + PhGA(cm) + CRP(mg/dL)$

The variables CDAI and SDAI denote Clinical Disease Activity Index and Simplified Disease Activity Index, respectively. For all composite outcomes, higher scores correspond to higher disease severity.

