3.1.6.1. ACR20, ACR50, ACR70, ACR90 outcomes

For a given level of response of x% (x=20,50,70,90) the study participant will be declared a responder if the following three criteria are satisfied:

1. A decrease by x% or more from the baseline in the number of tender joints (TJC68).
2. A decrease by x% or more from the baseline in the number of swollen joints (SJG66).
3. A decrease by x% or more from the baseline in three of the following five variables (see [Table 3](#))
 - a. PhGA
 - b. PAAP
 - c. PtGA
 - d. HAQ-DI
 - e. CRP or ESR

Also, the decrease in either of the lab measures CRP or ESR is sufficient for satisfying requirement 3e.

CCI

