5.3. Analyses of Binary Data

The estimands E2, E2*, and E3 are described in the [Section 2.1](#). The analyses for the estimands E2, E3, are based on the mITT data set while the analysis for the estimand E2* is based on the sensitivity data set. We denote the analyses of interest by the names of the corresponding estimands and denote the analyses based on descriptive statistics by D2, D3. The analyses names, data sets and analyses methods are listed in the Table 9.

Table 9. Analyses of Binary Data

Analysis Name	Data Set	Analytic Approach
E2	mITT	BSC + CZ (ratio of probabilities) + NRI
E2*	Sensitivity data set (SNS)	BSC + CZ (ratio of probabilities) + NRI
E3	mITT	BSC + CZ (difference of probabilities) + NRI
D2	mITT	BSC + CZ (ratio of probabilities) + NOIMP
D3	mITT	BSC + CZ (difference of probabilities) + NOIMP

*BSC+CZ= Blyth-Still-Casella + Chan and Zhang, NRI- non-responder imputation, NOIMP-no imputation.

We will use the Blyth-Still-Casella (Blyth and Still (1983)⁵ and Casella (1986)⁶) method for the estimation of the probability of response at a given visit and a given treatment arm and Chan and Zhang (Chan and Zhang, 1999)⁷ method for comparison of the probability of response across the treatment arms. For the E2, E2* and E3 analyses we will use the non-responder imputation treating missing value of the binary outcome as non-response with the exception of the two special cases of the reason for missing data. These special reasons for missing data include missingness related to the COVID infection (either patient illness or COVID-related problem of attending the visit) and missingness when subject attended the visit but some of the components for the calculation of the outcome (eg, ACR20) are missing. The observations that are missing for these special reasons will be excluded from the calculation of the probabilities of response at a given visit.

The p-values and 90% confidence intervals will be reported for the E2 and E3 analysis of key secondary and secondary efficacy outcomes for the comparisons of combination arms with tofacitinib arm. Only the confidence intervals with 90% coverage will be used for all other analyses of binary outcomes.

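### Attendees whose ACR or remission status is already settled by the observed components are set to missing and dropped from the responder rates

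*SAP*

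**What the plan says.** Three pieces of text act together.

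- **Composite rule.** After Table 4, SAP 3.1.4 states: "If any of the component of the score is missing, then the composite score is assigned to a missing value".
- **Exception to non-responder imputation (NRI).** In SAP 5.3, for the E2, E2* and E3 analyses, a missing binary outcome counts as non-response with two exceptions. One is COVID-related. The other is "missingness when subject attended the visit but some of the components for the calculation of the outcome (eg, ACR20) are missing".
- **Consequence.** Protocol 9.4.1 gives it for the key secondary endpoint: "The observations that are missing for these special reasons will be excluded from the calculation of the probabilities of response at a given visit". The synopsis, protocol 9.2.2 and SAP 5.3 say the same.

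The outcome definitions are as follows.

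- **DAS28-CRP** (SAP 3.1.5) is "0.56\sqrt{TJC28} + 0.28\sqrt{SJC28} + 0.36\ln(CRP, mg/l + 1) + 0.014PtGA(mm) + 0.96". Remission is a score below 2.6 (protocol 8.1.2.1).
- **ACRx** (SAP 3.1.6.1): "the study participant will be declared a responder if the following three criteria are satisfied". The first is "A decrease by x% or more from the baseline in the number of tender joints (TJC68"), the second is the same for swollen joints, and the third is "A decrease by x% or more from the baseline in three of the following five variables". For the laboratory item, a sufficient fall in either CRP or ESR is enough.

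No readable text classifies a participant from the components that were observed. Parts of SAP 3.1.6 and the appendices are redacted.

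**The concern.** Neither binary outcome needs every component to be known. DAS28-CRP is a constant plus terms that cannot be negative, so the observed terms give a floor for the score. ACR response requires all three criteria, so one failed criterion settles it. Within the third criterion, three passes or three failures out of five also settle it.

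Under the written rules these participants are treated as having no outcome and leave both numerator and denominator. Someone who misses the visit for a non-COVID reason is counted as a failure, while someone who attends with a demonstrably failed joint count and one unanswered item is not counted at all. E2 and E3 target everyone treated, and dropping people whose outcome is known moves away from that target without need. The key secondary endpoint and all four ACR endpoints are affected.

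**Working it through.** **Plan's own figure.** Protocol 9.2.2 gives about 84% power for 44.2% v 26% (ratio 1.7), one-sided 0.05, with no missing observations; 9.2.1 gives about 100 per arm. On the log-ratio scale, SE = √(0.74/26 + 0.558/44.2) = 0.203 and ln 1.7 = 0.531, so z = 0.531/0.203 − 1.645 ≈ 0.97 and power is 83.5%. A pooled two-proportion test gives 85.8%. The planning figure reproduces.

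**DAS28-CRP with a component missing.** Set the missing term to zero to get the floor.

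- hsCRP missing, TJC28 4, SJC28 4, PtGA 30 mm: 0.56×2 + 0.28×2 + 0.014×30 + 0.96 = 3.06. Certain non-remission.
- TJC28 = 9, nothing else known: 0.56×3 + 0.96 = 2.64. Certain non-remission. TJC28 = 8 gives 2.54, which is not enough alone.
- PtGA missing, TJC28 2, SJC28 2, CRP 5 mg/L: 0.79 + 0.40 + 0.36×ln 6 + 0.96 = 2.79. Certain non-remission.

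The reverse is rare. CRP has no upper limit, so remission can never be proven when hsCRP is missing. With PtGA missing its term can reach 1.40, so with zero joint counts remission is certain only if 0.36×ln(CRP+1) < 2.6 − 0.96 − 1.40 = 0.24, that is, CRP below about 0.95 mg/L.

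**ACRx with one of the five other items missing.** The outcome is:

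- settled non-response if either joint count fails, or if at most one of the four observed items passes;
- settled response if both joint counts pass and at least three of the four observed items pass;
- undetermined only if both joint counts pass and exactly two of the four pass.

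The rule drops all three groups, so settled responders are lost as well as settled non-responders.

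**Effect on the remission rates.** The documents give no frequency, so the dropped share is an assumption. Two patterns bracket the problem.

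*Pattern A: all dropped attendees are non-remitters.* The reported rate is p/(1−m).

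| m dropped | Rates, equal m in both arms | Difference (points) | Ratio, equal m | Ratio, combination arm only | Ratio, tofacitinib arm only |
|---|---|---|---|---|---|
| 0% | 26.0 v 44.2% | 18.2 | 1.70 | 1.70 | 1.70 |
| 2% | 26.5 v 45.1% | 18.6 | 1.70 | 1.73 | 1.67 |
| 5% | 27.4 v 46.5% | 19.2 | 1.70 | 1.79 | 1.62 |
| 10% | 28.9 v 49.1% | 20.2 | 1.70 | 1.89 | 1.53 |

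*Pattern B: hsCRP is lost unrelated to outcome.* Assume 18 of 100 are NRI non-responders (the Week 12 dropout in protocol 9.2.1, borrowed for Week 24). The combination arm then has 82 attendees, of whom 44.2/82 = 53.9% remit. Five random losses in that arm remove about 2.7 remitters and 2.3 non-remitters. With tofacitinib at 26%:

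- Written rule: 41.5/95 = 43.7%, ratio 1.68.
- Settled failures kept, undetermined excluded (taking all 2.3 non-remitters as provable): 41.5/97.3 = 42.7%, ratio 1.64.
- Settled failures kept, undetermined counted as non-responders: 41.5/100 = 41.5%, ratio 1.60.

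If the same loss occurs in both arms, the written rule multiplies each rate by the same factor and the ratio stays at 1.70.

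**The case against.** A reader might infer that the rule inflates response rates and favours the combinations, for instance by moving the ratio from 1.70 to 1.79. The documents do not support that. The rule drops every attendee with a missing component, remitters included. That only non-remission can be proven without hsCRP does not mean that only non-remitters are dropped. The 1.79 needs all the losses to be non-remitters and all to fall in the combination arm. The trial is double-blind, with one visit schedule and matched tablets, and nothing in the documents points to such an imbalance. Loss in the tofacitinib arm alone would lower the ratio. For ACR, settled responders are dropped too, so no net direction can be claimed.

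The number affected may also be small. Protocol 9.2.2 expects this, and under protocol 8.11 participants who do not meet ACR20 from Week 12 stop treatment and later leave the study. Many clear failures will therefore miss Week 24 and already count as non-responders.

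Excluding partial data at attended visits is written consistently in four places and looks deliberate. Pattern B shows that replacing it with NRI can move the remission estimate further from the planning value. Choosing between the two for undetermined attendees is a judgement.

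Finally, a derivation rule may sit in redacted text, and letting CRP or ESR satisfy the laboratory item suggests that the any-component rule was not meant literally for ACR. If so, SAP 3.1.4 and 5.3 still need to say it, because read as they stand they discard the participant.

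All of this limits size and direction. None of it is a reason to call a settled outcome missing.

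**Conclusion.** The concern holds as a derivation gap. On the readable text, attendees whose observed components already determine ACR response, ACR non-response or DAS28-CRP non-remission are removed from the responder rates. The case is clearest for ACR, where with one item missing only one specific combination of results is undetermined.

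The size is unknown and probably small. Absolute rates and the E3 differences are too high if the dropped attendees are mainly non-responders. They change little if missingness is unrelated to outcome. The direction for ACR is not fixed. The key secondary ratio shifts materially only if missingness differs between arms; with equal shares it stays at 1.70 under both patterns as the rule is written. These figures rest on assumed dropped shares of 2% to 10%, on five losses in Pattern B, and on the 18% dropout borrowed from Week 12.

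**What to change.** In SAP 3.1.4 and 5.3, and in protocol 9.4.1:

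1. Derive binary status from the observed components first. Assign non-response or response whenever they already settle it. For the ACR laboratory item, accept either CRP or ESR, as SAP 3.1.6.1 does. Treat the outcome as missing only when it is undetermined.
2. Report, by arm and visit, how many attendees with a missing component were settled as responders, settled as non-responders, or undetermined.
3. For DAS28-CRP remission, do not silently replace the exclusion with NRI. Present both handlings of undetermined attendees, exclusion and NRI, and name in advance which is the main analysis and which the sensitivity analysis. This is needed because remission cannot be proven without hsCRP, so keeping settled failures while excluding the rest is itself one-sided.

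The cost is a wording change and a few lines of derivation code, using data already collected. The downside is slightly lower remission rates.

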3.1.5. Continuous Composite Measures of Efficacy: DAS28-CRP, DAS28-ESR, CDAI, SDAI

Table 5. Continuous Composite Outcomes

Variable	Calculation
DAS28-CRP	$0.56\sqrt{TJC28} + 0.28\sqrt{SJC28} + 0.36\ln(CRP, mg/l + 1) + 0.014PtGA(mm) + 0.96$
DAS28-ESR	$0.56\sqrt{TJC28} + 0.28\sqrt{SJC28} + 0.70\ln(ESR, \frac{mm}{hr}) + 0.014PtGA(mm)$
CDAI	$TJC28 + SJC28 + PtGA(cm) + PhGA(cm)$
SDAI	$TJC28 + SJC28 + PtGA(cm) + PhGA(cm) + CRP(mg/dL)$

The variables CDAI and SDAI denote Clinical Disease Activity Index and Simplified Disease Activity Index, respectively. For all composite outcomes, higher scores correspond to higher disease severity.

3.1.6. Binary Composite Measures of Efficacy

The following binary measures of efficacy will be evaluated.

3.1.6.1. ACR20, ACR50, ACR70, ACR90 outcomes

For a given level of response of x% (x=20,50,70,90) the study participant will be declared a responder if the following three criteria are satisfied:

1. A decrease by x% or more from the baseline in the number of tender joints (TJC68).
2. A decrease by x% or more from the baseline in the number of swollen joints (SJG66).
3. A decrease by x% or more from the baseline in three of the following five variables (see [Table 3](#))
 - a. PhGA
 - b. PAAP
 - c. PtGA
 - d. HAQ-DI
 - e. CRP or ESR

Also, the decrease in either of the lab measures CRP or ESR is sufficient for satisfying requirement 3e.

CCI

3.2. Baseline Variables

Unless specifically stated otherwise, the baseline value is defined as the last non-missing measurement collected prior to the first administration of study drug at Day 1.

Baseline value will be used as a covariate in statistical models for change from baseline in efficacy endpoints to adjust for baseline disease severity.

